- For patients undergoing systemic treatment (alone or in combination with targeted treatment): If on post-treatment follow-up imaging within 3-12

months, lesions seen on CT or MRI decrease by more than 30% in long axis diameter and PSA declines by more than 50%.

- If PSA increases by more than 50% on systemic therapy, then a increase in the size of lesion by more than 20% will be considered a true positive lesion.

- In subjects with localized suspected lesions(s) receiving targeted treatment without concomitant systemic treatment there are two ways to meet true positive disease:

- If the subject demonstrates a decrease of PSA by greater than 50% after targeted treatment [OR]
- If on post-treatment follow-up imaging within 3-12 months, lesions seen on CT or MRI decrease by more than 30% in long axis diameter (with a minimum of 3 mm in change in size)

- For untreated patients: If on follow-up imaging within 3-12 months, lesions seen on CT or MRI increase by more than 20% in long axis diameter (with a minimum of 3 mm in change in size).

(2) False positive:

- For patients undergoing systemic treatment (alone or in combination with targeted treatment): If on post-treatment follow-up imaging within 3-12 months, lesions seen on CT or MRI increase by more than 20% in long axis diameter and PSA decreases by more than 50%.

- In subjects with localized suspected lesions(s) receiving targeted treatment without concomitant systemic treatment there are two ways to meet false positive disease:

- If the subject does not demonstrate a decrease of PSA by greater than 50% after targeted treatment [OR]
- If on post-treatment follow-up imaging within 3-12 months, lesions seen on CT or MRI increase by more than 20% in long axis diameter (with a minimum of 3 mm in change in size)

- For untreated patients: If on follow-up imaging within 3-12 months, lesions seen on CT or MRI decrease by more than 30% in long axis diameter (with a minimum of 3 mm in change in size).

(3) If all regions in a patient/region do not meet criteria for either True positive or False positive disease, then the patient/region will be considered inevaluable for primary endpoint.

iii) ⁶⁸Ga-PSMA-11 positive bone lesions will be considered:

(1) True positive:

- If there was a corresponding positive sclerotic lesion on the CT portion of the ^{68}Ga -PSMA-11 PET or on a separate CT obtained ≤ 30 days before or after the PET/CT in the same location as the PSMA uptake.

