- If there is focal uptake seen in the same location as the PSMA uptake on the baseline bone scan performed within one month of ^{68}Ga -PSMA-11 PET.
- If there is a lesion noted in the same location as the PSMA uptake on the initial MRI performed within one month of ^{68}Ga -PSMA-11 PET.
- If within 12 months follow-up CT demonstrates development of sclerosis in the same location as the PSMA uptake.
- If within 12 months follow-up MRI demonstrates a new bone lesion in the same location as the PSMA uptake.
- If within 12 months follow-up bone scan demonstrates new focal uptake in the same location as the PSMA uptake.
- In subjects with localized suspected bone lesion(s) receiving targeted treatment without concomitant systemic treatment:
 - o If the subject demonstrates a decrease of PSA by greater than 50% after targeted treatment.

(2) False positive:

- In subjects with localized suspected bone lesion(s) receiving targeted treatment without concomitant systemic treatment:
 - o If the subject does not demonstrate a decrease of PSA by greater than 50% after targeted treatment with curative intent (ie non-palliative radiation).
- If ^{68}Ga -PSMA-11 positive bone lesions do not meet the criteria for true positive findings, and appropriate correlative and follow-up imaging was acquired.

(3) If bone lesions do not meet criteria for either true positive or false positive disease listed above, then the patient/region will be considered inevaluable for primary endpoint.

iv) ^{68}Ga -PSMA-11 positive prostate bed and prostate lesions will be considered:

(1) True positive:

- For patients undergoing systemic treatment (alone or in combination with targeted treatment): If on post-treatment follow-up imaging within 3-12 months, lesions seen on CT or MRI decrease by more than 30% in long axis diameter
- In subjects with localized suspected lesions(s) receiving targeted treatment without concomitant systemic treatment there are two ways to meet true positive disease:

- If the subject demonstrates a decrease of PSA by greater than 50% after targeted treatment [OR]
- If on post-treatment follow-up imaging within 3-12 months, lesions seen on CT or MRI decrease by more than 30% in long axis diameter (with a minimum of 3 mm in change in size)

- For untreated patients: If on follow-up imaging within 3-12 months, lesions seen on CT or MRI increase by more than 20% in long axis diameter (with a minimum of 3 mm in change in size).

(2) False positive:

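### Both CT routes to a true-positive bone lesion require sclerosis and bone has no growth rule, so a new or enlarging lytic lesion assessed by CT alone can be scored as a false positive

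*Combined protocol and SAP*

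**What the plan says.** Section 8.3.2 b) iii) lists the ways in which a PSMA-positive bone lesion is validated.

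- **CT, baseline:** "If there was a corresponding positive sclerotic lesion on the CT portion of the" PET, or on a separate CT within 30 days of it.
- **CT, follow-up:** "If within 12 months follow-up CT demonstrates development of sclerosis in the same location as the PSMA uptake".
- **MRI, baseline:** "If there is a lesion noted in the same location as the PSMA uptake on the initial MRI performed within one month of" the PET. No morphology is required.
- **MRI, follow-up:** "If within 12 months follow-up MRI demonstrates a new bone lesion in the same location as the PSMA uptake".
- **Bone scan:** focal uptake at the site at baseline, or new focal uptake on follow-up.
- **PSA:** a fall of more than 50%, but only after targeted treatment without systemic treatment.

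One false-positive bullet is residual. It applies if "positive bone lesions do not meet the criteria for true positive findings, and appropriate correlative and follow-up imaging was acquired". A lesion that meets neither list is inevaluable under iii) (3).

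Section 8.3.2 b) allows follow-up by CT, MRI and/or bone scan and prefers the modality of the initial staging. Section 6.1.3 leaves follow-up imaging to institutional standard of care. CT-only follow-up is therefore within the plan.

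**The concern.** The two CT bullets recognise one appearance, sclerosis. A lytic lesion at the PSMA site, even one that appears or grows during follow-up, satisfies neither unless it later turns sclerotic. In the other tissues an incomplete true-positive list does little harm, because an unmatched lesion becomes inevaluable. Bone alone has a bullet that can turn failure to match the true-positive list into a false positive.

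The label can then depend on which scan was done and what the lesion looks like, rather than on whether it is cancer. At stake are PPV for the bone region (a secondary endpoint) and, in men with no true-positive region elsewhere, per-patient PPV and to a small extent per-patient sensitivity.

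**Working it through.** **No plan figure to reproduce.** The documents state neither the share of bone lesions that are lytic nor the share followed by CT alone. The check is a trace of the rules, followed by an illustration on stated assumptions.

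**Step 1: trace one case.** Take an untreated man with a PSMA-positive bone site that is lytic on the PET's CT and is larger and still lytic on CT at six months. He has no MRI, no bone-scan focus and no pathology.

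| Route in b) iii) (1) | Requires | Met? |
|---|---|---|
| CT, baseline | sclerotic lesion | No |
| Bone scan, baseline | focal uptake at the site | No |
| MRI, baseline | any lesion at the site | Not done |
| CT, follow-up | sclerosis developing | No |
| MRI, follow-up | new lesion | Not done |
| Bone scan, follow-up | new focal uptake | No |
| PSA | fall >50% after targeted treatment alone | Does not apply |

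No true-positive rule is met. If his imaging is judged appropriate, the residual bullet makes the lesion a false positive. If not, iii) (3) makes it inevaluable. No route makes it a true positive.

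**Step 2: compare tissues.** In an untreated man, growth on CT or MRI of more than 20% with at least 3 mm is *true* positive for lymph nodes (short axis), visceral lesions (long axis) and prostate bed (long axis). For nodes and viscera, growth of more than 20% with PSA rising by more than 50% on systemic therapy is also true positive. Bone has neither rule.

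**Step 3: compare modalities.** A baseline MRI within one month showing any lesion at the site would make the same lesion true positive. A follow-up MRI would do so only if the lesion were new, and this one was already visible on the PET's CT.

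**Step 4: illustrate the size.** Inputs:

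- 375 men with biopsy or imaging follow-up, and 11% with bone metastases (section 8.2.1).
- 87% for the share of bone positives that are true. This is an assumption. Section 8.2.1 gives 87% for first-cohort biopsies in all regions and calls it specificity. It also reports no true negatives, so I use it as a PPV.
- *l* = share of true bone-positive men whose only bone lesions are lytic, are assessed by CT alone, have no other confirming route, and are called false positive. The range 5-20% is assumed.

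Bone-positive men: 0.11 × 375 = 41.25. True bone positives: 41.25 × 0.87 = 35.9, about 36.

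Men relabelled = 35.9 × *l*. Bone PPV = 0.87 × (1 − *l*). Bone sensitivity, starting from the 70% hypothesised per region, = 0.70(1 − *l*) / [0.70(1 − *l*) + 0.30], because a false positive leaves both numerator and denominator.

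| *l* | Men relabelled | Bone PPV | Bone sensitivity |
|---|---|---|---|
| 0 | 0 | 87% | 70% |
| 5% | 1.8 | 82.7% | 68.9% |
| 10% | 3.6 | 78.3% | 67.7% |
| 20% | 7.2 | 69.6% | 65.1% |

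**Step 5: patient level.** Suppose all 375 men are diseased and 70% are detected: 0.70 × 375 = 262.5 true positives. If all 7.2 men at *l* = 20% had no true-positive region elsewhere, sensitivity would be (262.5 − 7.2) / (375 − 7.2) = 255.3 / 367.8 = 69.4%.

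**The case against.** The strongest reply is that the plan contains several escapes.

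- **Classification as false positive is not automatic.** A reader might infer that any lytic lesion seen on CT becomes a false positive. The text does not support that. Every MRI, bone-scan, PSA and pathology route must fail or be absent, and the imaging must be judged appropriate. Otherwise the lesion is inevaluable.
- **MRI is not a general rescue.** A reader might infer that the lesion would be true positive had MRI been used instead of CT. That holds only for a baseline MRI.
- **Investigators may deviate.** Section 8.3.2 d) presents the criteria as a guide and allows recorded departures in individual patients. An enlarging lytic lesion is an obvious candidate.
- **Other findings protect the region and the patient.** Where there is no pathology, one imaging-confirmed bone lesion makes the region true positive despite a false-positive lesion in it. An imaging-based false-positive region does not undo a true-positive region elsewhere. A share of lesions therefore cannot be read as a share of men.

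All four points stand, and they limit how often the problem bites. They do not close the gap. *Appropriate* is undefined, and CT-only follow-up is permitted. The PSA route does not reach untreated or systemically treated men. Section 8.3.2 c) itself warns of frequent false-negative bone biopsies, and section 8.2.1 expects biopsy rates to fall. The deviation clause substitutes case-by-case judgement for a rule, while section 8.1.2 leaves the local follow-up readers unblinded to all results.

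**Conclusion.** The concern holds in a limited form. A new or enlarging lytic lesion at the PSMA site, assessed by CT with no other confirming result, cannot be a true positive under the written bone criteria and may be a false positive. In an untreated man, the same growth in any other tissue would be a true positive.

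On the assumptions shown, about 2-7 of roughly 36 true bone-positive men would be relabelled, and bone PPV would read at worst 83%-70% instead of 87%. This is an upper bound, not an expected effect: the 5-20% is assumed, the 87% is not a bone figure, and every affected lesion is taken as called false positive rather than inevaluable.

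A reader might infer that the primary endpoint is seriously threatened. The figures do not support that. Per-patient sensitivity would move from 70% to about 69.4% in the worst illustrated case. That matters only for a reader close to the 70% success mark in section 8.3.2. The main effect is on bone-region PPV.

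**What to change.** Make three text changes in section 8.3.2 b) iii):

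1. Add to (1) a CT route. A lytic lesion at the PSMA site is true positive if, on follow-up CT within 12 months, it is new or has increased by more than 20% with at least 3 mm. Apply the treatment and PSA conditions that the plan already uses for visceral growth: untreated, or PSA rising by more than 50% on systemic therapy. Growth with a PSA fall of more than 50% on systemic treatment, which is false positive for viscera, stays outside the route.
2. State in (2) that a lesion meeting this route cannot enter the residual false-positive bullet.
3. Define in (2) what counts as appropriate correlative and follow-up imaging for bone, including whether CT alone suffices.

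Stable lytic lesions should not be moved wholesale to inevaluable. That would remove possible genuine false positives and could bias PPV upward. Mixed lesions need no new route, since their sclerotic part arguably meets the existing baseline CT bullet.

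The cost is one bullet, one exclusion and one definition, applied to CTs already collected. The downside is that a few benign lesions that grow could be counted as true positive.

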 - For patients undergoing needle biopsy: Images of the procedure will be reviewed to determine if the correct node was biopsied.
 1. If the correct node was biopsied, then a negative biopsy will be considered a False Positive.
 2. If the incorrect node was biopsied, then follow-up imaging as described above will be performed.
- (b) Bone lesions: Given the high rate of false negative biopsies for osseous metastases in patients with prostate cancer, patients with negative bone biopsies of PSMA PET positive lesions will be further evaluated:
- If pathology demonstrates an alternative diagnoses that is known to be PSMA positive (eg Renal Cell Carcinoma metastases, Paget's disease), then this will be considered a False Positive.
 - If pathology is indeterminate, then follow-up imaging as described above will be performed.
- (3) Although not routinely performed during standard practice, immunohistochemical staining for PSMA of tumor specimens (primary and lymph node metastases) may be performed, although not required.
- d) Definitions of True Positive, False Positive, True Negative, and False Negative patients and regions: Pathology will be considered superior to imaging and clinical follow-up when available as described below. Patient and region level classification will be performed for each blinded reader, and be reported separately. The following criteria serve as a guide for interpretation. However not all findings on a lesions, region and patient level can be detailed here and investigators may deviate from these criteria in individual patients. These will be recorded for each interpretation that is not described in this protocol for the definition of a region or patient.
- i) Patient level evaluation:
- (1) True positive patient: A single region in a patient contains a true positive node either by pathology or imaging/clinical follow-up.

- (a) For a patient to be considered a True Positive, only one region is required to have a true positive lesion as described above, unless one region is categorized as a false positive based on pathology. This means that a single pathology false positive region outweighs regions with imaging/clinical follow-up true positive disease.
 - (b) A patient will be considered a True Positive if one region contains a lesion that is True Positive, even if other regions are categorized as inevaluable or false positive based on imaging or clinical follow-up.

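### Without diagnostic pathology, the baseline bone True Positive rules have no exclusion for a benign cause, so a lesion such as Paget's disease counts as verified metastasis if it is only imaged

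*Combined protocol and SAP*

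**What the plan says.** All the rules are in section 8.3.2.

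- **Baseline True Positive items, b) iii) (1).** Any one of three co-located findings is enough. For CT: "If there was a corresponding positive sclerotic lesion on the CT portion of the" PET study, or on a separate CT within 30 days; the word positive is not defined. For bone scan: "If there is focal uptake seen in the same location as the PSMA uptake on the baseline bone scan". For MRI: "If there is a lesion noted in the same location as the PSMA uptake on the initial MRI". The last two must fall within one month of the PET.
- **Follow-up True Positive items, b) iii) (1).** These need change. For CT: "If within 12 months follow-up CT demonstrates development of sclerosis in the same location as the PSMA uptake". For bone scan: "If within 12 months follow-up bone scan demonstrates new focal uptake in the same location as the PSMA uptake". The MRI item likewise asks for a new lesion.
- **False Positive items, b) iii) (2).** One is residual: it covers lesions that "do not meet the criteria for true positive findings, and appropriate correlative and follow-up imaging was acquired". The other covers lesions given curative-intent targeted treatment alone, where PSA does not fall by more than 50%.
- **Negative bone biopsy, c) ii) (2) (b).** The rule opens "If pathology demonstrates an alternative diagnoses that is known to be PSMA positive" and continues with its examples and label: "eg Renal Cell Carcinoma metastases, Paget's disease), then this will be considered a False Positive". An indeterminate biopsy goes back to the imaging rules.
- **Precedence, d).** Pathology outranks imaging where it exists. Investigators may depart from the criteria in individual patients, and such cases are recorded.

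**The concern.** The biopsy section shows that the authors know some non-prostate-cancer bone lesions take up PSMA-11, and that they want these counted as False Positive. The imaging section has no counterpart. It asks whether something is visible at the site, not what it is. Where a benign lesion has a visible correlate, its label then depends on whether a diagnostic biopsy was done.

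This matters because most lesions will be judged by imaging. Section 8.2.1 reports that 19% of patients in the first cohort had a biopsy after a positive scan, and expects that rate to fall. Bone is also the only region in which a static baseline finding is enough; nodes, visceral lesions and the prostate bed need a change in size or a PSA response. At stake is the credibility of bone-region PPV in a study meant to support approval.

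**Working it through.** The plan states no figure on this point, so the first check traces one lesion through the rules.

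**Step 1: rule trace.** Take a PSMA-positive Paget's lesion with a sclerotic, bone-scan or MRI correlate at baseline.

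| Situation | Rule that applies | Label |
|---|---|---|
| Biopsied, pathology shows Paget's | c) ii) (2) (b); pathology outranks imaging | False Positive |
| Not biopsied | b) iii) (1), baseline item | True Positive |
| Biopsied, indeterminate | returned to b) iii) | True Positive |
| No baseline correlate, nothing new at follow-up, appropriately imaged | b) iii) (2), residual item | False Positive |

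In the second and third rows the residual item cannot apply, because a True Positive item is already met. If the lesion also had curative-intent targeted treatment without the PSA fall, it meets a True Positive and a False Positive item together. No order is stated for a single lesion, although d) ii) lets True Positive prevail within a region on imaging or clinical evidence.

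**Step 2: bone PPV.** The documents give no benign share, so the inputs are assumptions. Let b be the share of PSMA-positive bone lesions that are benign, c the share of those with a qualifying correlate, and s the share of true metastases with one. Assume no pathology, no PSA-based classification, and every lesion evaluable.

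- True PPV = 1 − b.
- Reported PPV = (1 − b)s + bc.
- Part due to the missing exclusion = bc.

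For b from 5% to 30% and c from 50% to 100%, bc runs from 0.05 × 0.50 = 2.5 points to 0.30 × 1.00 = 30 points. At c = 80%:

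| b | bc | True PPV | Reported, s = 100% | Reported, s = 70% |
|---|---|---|---|---|
| 10% | 8 points | 90% | 90 + 8 = 98% | 63 + 8 = 71% |
| 30% | 24 points | 70% | 70 + 24 = 94% | 49 + 24 = 73% |

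The s = 70% column is lower because the residual item scores an appropriately imaged metastasis without a correlate as False Positive. The two errors cancel at s = 1 − bc/(1 − b), which is 1 − 0.08/0.90 = 91% and 1 − 0.24/0.70 = 66%. Below these values the net bias in PPV is downward.

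If 19% of the benign lesions had a diagnostic biopsy (the first cohort's patient-level rate, applied to bone as an assumption), the 8 and 24 points become 8 × 0.81 = 6.5 and 24 × 0.81 = 19.4.

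**Step 3: bone sensitivity.** Section 8.2.1 gives 375 patients with a reference standard and 11% with bone disease: 375 × 0.11 = 41.25 bone-positive. Assume a true bone sensitivity of 60%, so false negatives = 41.25(1 − b) × 0.4/0.6. With c = 100%, the reported value is 41.25/(41.25 + false negatives):

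- b = 5%: 41.25/67.4 = 61.2%
- b = 30%: 41.25/60.5 = 68.2%

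With c = 50% the values are 60.6% and 64.6%. These are generous to the concern: d) ii) leaves regions without PSMA-positive disease out of the regional analysis, which pushes regional sensitivity towards 100% whatever the bone rule says.

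**Step 4: per-patient sensitivity.** A mislabelled bone lesion matters only if no other region is True Positive. As an upper bound, suppose that holds for all of them. With c = 80%, 41.25 × 0.10 × 0.80 = 3.3 and 41.25 × 0.30 × 0.80 = 9.9 patients, about 3 to 10. Starting from an assumed 250/360 = 69.4%, the result is 253/363 = 69.7% or 260/370 = 70.3%, a rise of 0.3 to 0.8 points.

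**The case against.** The strongest reply is that composite reference standards commonly label biopsied and unbiopsied lesions differently, that pathology takes precedence here, and that section 8.3.2 d) calls its criteria a guide and allows recorded departures. An investigator who recognises Paget's disease on CT may override the label. Reader training on common pitfalls may also reduce such calls. This stands as mitigation. It does not close the gap, because the override is permitted and not required, and no rule directs anyone to look for a benign cause. Section 8.1.2 also has local follow-up readers told where the PSMA-positive lesions are, which makes a non-specific correlate easier to find.

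Three stronger readings are tempting, and the documents do not support them.

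- A reader might infer that every benign bone lesion is scored as metastasis on any imaging finding. Pathology-proven cases are False Positive, and the follow-up items need a new or developing finding, so stable Paget's disease already visible at baseline does not meet them.
- A reader might infer that bone PPV must be overstated by the full 8 to 24 points. That needs every true metastasis to have a correlate, and ignores biopsy and the PSA-based False Positive item.
- A reader might infer that the primary result is materially inflated. Step 4 does not show that.

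Nor do the documents say how common benign PSMA-avid bone lesions are, or which causes dominate; in bone they name only Paget's disease.

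**Conclusion.** The concern holds for PSMA-positive bone lesions without diagnostic pathology that have a baseline correlate, and for follow-up only where a benign finding is new. For these, the written rule gives a label opposite to the one the plan assigns once pathology is known.

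The error itself always favours the tracer. Its main effect is on bone-region PPV, a secondary endpoint without a success threshold: 2.5 to 30 points over the assumed ranges, before allowing for biopsy. The net bias in PPV may go either way, because metastases without a correlate can be scored False Positive. The upward effect on per-patient sensitivity is under about one point on the assumptions shown, so it would matter only if a reader's result lay within a point of the 70% criterion. None of these sizes can be fixed from the documents.

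**What to change.** In 8.3.2 b) iii) (1), state that a CT, MRI or bone-scan correlate does not qualify a lesion as True Positive when the imaging report gives a definite benign or alternative diagnosis at that site, for example Paget's disease. In b) iii) (2), score such a lesion as False Positive, in line with c) ii) (2) (b), with pathology still taking precedence.

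The change uses imaging that the rule already depends on. Section 6.1.3 provides only for collecting follow-up images or reports, so the plan should also say that baseline CT, MRI and bone-scan reports are collected. The cost is a slightly less favourable bone PPV. Benign lesions without a definite diagnosis would still count as True Positive, so the fix removes part of the error, not all of it.

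A broader condition, that each correlate must look suspicious for metastasis, is harder to defend: it adds a subjective call by local readers who are unblinded and know the PSMA-positive sites.

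### A bone lesion seen on bone scan or MRI more than one month from PET and still present at follow-up meets no bone-scan or MRI true-positive criterion, and can default to false positive

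*Combined protocol and SAP*

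**What the plan says.** The bone rules are in Section 8.3.2, Reference Standard Definition, part b) iii). The bone-scan and MRI routes to a true positive are:

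- Baseline bone scan: "focal uptake seen in the same location as the PSMA uptake on the baseline bone scan performed within one month of" PET.
- Baseline MRI: a lesion at the PSMA site "on the initial MRI performed within one month of" PET.
- Follow-up MRI: "If within 12 months follow-up MRI demonstrates a new bone lesion in the same location as the PSMA uptake".
- Follow-up bone scan: "If within 12 months follow-up bone scan demonstrates new focal uptake in the same location as the PSMA uptake".

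Three further routes do not depend on bone scan or MRI: sclerosis on the PET's own CT or on a CT within 30 days of it; sclerosis that develops on follow-up CT ("If within 12 months follow-up CT demonstrates development of sclerosis in the same location as the PSMA uptake"); and a PSA fall of more than 50% after targeted treatment given without systemic treatment. Part c) adds positive pathology.

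The second false-positive bullet for bone is a catch-all. It applies if PSMA-11 "positive bone lesions do not meet the criteria for true positive findings, and appropriate correlative and follow-up imaging was acquired". Only a bone lesion that escapes this bullet as well is inevaluable. Nodal, visceral and prostate-bed lesions have no such bullet; if they meet neither list they are inevaluable.

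Part d) calls the criteria a guide and lets investigators depart from them in individual patients, with the departure recorded.

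**The concern.** The bone-scan and MRI routes leave a hole between the one-month window and the word *new*. A lesion seen at the PSMA site six weeks before PET and seen again six months after it is outside the window and, read literally, is not new. The catch-all can then score it against PET.

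This ranks the evidence the wrong way round. One scan 29 days from PET gives a true positive with no follow-up required. Two concordant scans on either side of PET can give a false positive.

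The case is foreseeable. Neither the screening list (Section 6.1.1.1) nor Appendix 2 schedules a bone scan or MRI near PET, so the timing depends on routine care. Section 8.3.2 b) also prefers follow-up by the same modality as the initial work-up, and repeating an older positive scan produces exactly a persisting lesion.

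Two terms add to the problem. *New* has no stated comparator, so where no earlier scan exists it cannot be shown at all. What counts as appropriate correlative imaging is not defined, so the choice between false positive and inevaluable is left open.

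At stake is bone-region PPV and, through lost true positives, bone-region sensitivity.

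**Working it through.** **Step 1: run the cases through the rules.** All concern a PSMA-positive bone lesion. In A and B it was seen on bone scan or MRI six weeks before PET and persists at follow-up, with no CT sclerosis, no qualifying PSA fall and no biopsy.

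| Case | Label under Section 8.3.2 |
|---|---|
| A. Imaging judged appropriate | False positive |
| B. Imaging not judged appropriate | Inevaluable |
| C. As A, but the earlier scan was 29 days before PET | True positive |
| D. As A, but sclerotic on the PET's CT or on a CT within 30 days | True positive |
| E. As A, but sclerosis develops on follow-up CT | True positive |
| F. As A, but PSA falls more than 50% after targeted treatment alone | True positive |
| G. As A, but biopsy positive | True positive |

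A and C differ only in the date of the earlier scan.

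**Step 2: number of bone-positive men.** The plan gives no bone PPV to reproduce. Its 375 does reproduce: 75 / 0.20 = 375 (Section 8.2.1). The same section expects bone disease in 11% of men. Applying that share to the 375 with a reference standard (an assumption) gives 0.11 × 375 = 41.25, about 41.

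**Step 3: starting PPV.** Section 8.2.1 reports 87% from biopsies in the first cohort, all regions together, and calls it specificity. The same section reports no true negatives, so the figure can only behave as a PPV. Used here as an assumption for bone: 0.87 × 41 = 35.7, about 36 true. Starting PPV = 36/41 = 88%.

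**Step 4: affected men.** The documents give no share. Assumption: 10% to 30% of 41, or 4 to 12 men, all truly positive.

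| Affected | All false positive (case A) | All inevaluable (case B) |
|---|---|---|
| 0 | 36/41 = 88% | 36/41 = 88% |
| 4 | 32/41 = 78% | 32/37 = 86% |
| 12 | 24/41 = 59% | 24/29 = 83% |

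On the first branch each man costs 1/41 = 2.4 points. On the second the whole loss is about 1 to 5 points.

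**Step 5: bone-region sensitivity.** Sensitivity is TP/(TP + FN), and both branches remove the same true positives. If it starts near the plan's hypothesised 70%, FN = 36 × 0.3/0.7 = 15.4, about 15. Then 36/51 = 71% becomes 32/47 = 68% or 24/39 = 62%. That is a smaller move than PPV makes on the false-positive branch, although not smaller than on the inevaluable branch. In practice 15 is probably high: part d) ii) makes a region false negative only on positive pathology, and the first cohort had no biopsy false negatives. With no false negatives the estimate does not move and only precision is lost.

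**Step 6: patient level.** Under part d) i) a true-positive region outweighs an imaging-based false positive elsewhere. Only men with no other true-positive region change label.

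**The case against.** A reader might infer that a persisting bone metastasis can never be a true positive. The documents do not support that. Cases D to G are all open to it, and pathology outranks imaging. In a PET/MRI patient the MRI acquired with the PET could arguably meet the one-month MRI bullet. These routes are partial: the PSA route excludes men on systemic treatment, and biopsy is done only as clinically indicated.

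The deviation clause also stands. A lesion confirmed on two scans is an obvious candidate for it, so the default is not automatic. It is a weak substitute for a rule, because Section 8.1.2 leaves the local follow-up readers unblinded and tells them where PET was positive. Case-by-case rescue could differ by site and lean towards PET.

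It is fair to add that a scan outside the plan's own one-month window may be judged not appropriate. The lesion is then inevaluable and the PPV loss is small. The 78% to 59% range is one branch only, and the affected share has no source in the documents.

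Finally, a loose repair would bias the other way. Counting any follow-up finding as confirmation, or allowing no false positive wherever some scan shows something, would let stable benign lesions confirm PET. That objection is sound and limits the fix.

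**Conclusion.** The gap is real and follows from the wording: no bone-scan or MRI criterion covers a lesion that predates the one-month window and persists. Such a lesion is a false positive or inevaluable unless another route or a recorded deviation applies, although a single scan nearer PET would have confirmed it.

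The main effect is a downward bias in bone-region PPV, which is secondary. With 41 bone-positive men, 36 assumed true and 4 to 12 assumed affected, PPV falls from 88% to between 78% and 59% if all are scored false positive, or to about 86% to 83% if all are inevaluable. A mixture would lie between. Bone-region sensitivity moves less than PPV does on the false-positive branch, and hardly at all if regional false negatives are few.

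A reader might also infer that the primary success rule is compromised. The documents do not show that. Success is judged on per-patient sensitivity, and only men with no other true-positive region are touched.

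**What to change.** Amend Section 8.3.2 b) iii) before lesions are classified:

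1. Count a bone-scan or MRI lesion at the PSMA site on an earlier scan outside the one-month window as a true positive if follow-up by the same modality shows the same lesion persisting or progressing, and it is not described as benign. This is no laxer than the existing rule, which accepts one scan within a month and asks for no follow-up.
2. Define the comparator for *new*. Where no earlier scan exists, treat a follow-up finding as inevaluable unless another criterion is met.
3. Limit the default false-positive bullet to sites where adequate baseline and follow-up imaging show no correlate, or show an alternative benign diagnosis, and say what imaging is adequate. Leave the remaining lesions inevaluable, as for the other lesion types.
4. Report bone PPV a second time with the lesions admitted under item 1 treated as inevaluable.

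The cost is mainly wording. Older scans or their reports must also be collected where they exist; Section 6.1.3 provides only for follow-up images or reports. The downside is that some stable benign lesions may be counted as true positives, and item 4 shows how much that matters.
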